Objectives:	
Primary Objective: Compare the safety and accuracy/efficacy of low dose Y90 resin microspheres and MAA in predicting the actual dose delivered to the tumor, liver, and lung after Y90 therapy.
 
Secondary Objectives:
 
 1. Optimize low dose Y90 techniques in predicting TNR and LSF. 2. Identify tumor dose response thresholds (TDRT) and tumor dose distribution in patients with HCC treated with Y90 resin microspheres.
Endpoints:	
Primary Endpoint: The lung shunt fraction (LSF) and tumor to normal liver activity ration (TNR).
 
Secondary Endpoints:
 
 1. Monitoring all grades of Y90 related toxicity

	2. Tumor response evaluation at 1, 3 and 6 months and determination TDRT
Study Population:	N=30 patients with hepatocellular carcinoma (HCC), male or female, =>18 years of age, all ethnicities, ECOG <2, and generally local patients referred to Winship.
Phase:	2
Description of Sites/Facilities Enrolling Participants:	All patients will be recruited at Emory Interventional Radiology Clinics after they have been discussed and referred through multidisciplinary liver tumor boards. Only patients that are found to be ideal candidates for Y90 radioembolization at tumor boards will be considered for recruitment. Emory University Hospital and Emory University Hospital Midtown will be the clinical sites to perform the study.

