Description of Study Intervention:	In this study, patients with HCC who are found to be ideal candidates for HCC and who would fit our inclusion criteria, described below, will be recruited. Patients will undergo standard of care mapping study with ⁹⁹ TC-MAA to plan for Y90 radioembolization therapy. The additional, non-standard of care, intervention will be to do a second mapping study using low-dose Y90 (15 mCi) before the therapeutic Y90 radioembolization. The distribution of MAA in terms of lung shunt fraction (LSF) and tumor to normal liver activity ratio (TNR) will be compared to that of low-dose Y90. The treatment planning will be performed using standard of care MAA biodistribution using partition dosimetry model. After administration of therapeutic Y90 dose, the actual dose delivered to tumor, non-tumoral liver (NTL) and lungs will be compared to the dose predicted by MAA and low-dose Y90. The patients will be followed-up clinically and with imaging at 1, 3 and 6 months to determine tumor response, potential treatment related toxicity and to determine TDRT.
Study Duration:	24 months
Participant Duration:	6 months

[figure not shown]

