The above observations suggest that the use of mean absorbed dose for the entirety of the tumor is inaccurate for determining TDR because a single small area of microsphere concentration may spuriously suggest that a tumoricidal dose has been achieved. We believe that wide ranges in previously reported TDR thresholds are largely explainable by disparities in dosimetry methodology used by different investigators, the inadequacy of currently employed Y90 RE dosimetric techniques in addressing the complex interactions between the tumor microvasculature, RE devices (glass vs. resin) and resulting radioactive microsphere biodistribution[7, 30]. Other factors including the indirect and continuous Bremsstrahlung radiation spectrum detected on SPECT and alteration in flow biomechanics by surrogate injection may play secondary roles[7].

Manufacturer recommended Y90 RE dosimetry models include empiric (set dose of radiation delivered to liver lobe regardless of tumor type) and a variation of the body surface area method which can additionally factor in tumor volume as determined by cross-sectional imaging[31, 32]. Not only do these methods rely on variables that poorly correlate to absorbed dose prediction and Y90 microsphere biodistribution, they also fail to consider the highly unique tumor micro- and macro-environment. To date, the partition model is the most studied personalized dosimetry model, requiring the determination of MAA uptake TNR during the shunt study using

SPECT/CT[33]. In the partition model, MAA is assumed to mirror Y90 biodistribution and to distribute uniformly within the liver tumor and NTL, but at different concentrations. Such assumptions facilitate calculation of Y90 doses separately for the tumor and NTL which can be used to plan treatments based on dose limits that are thought to minimize pulmonary and hepatic toxicities[33, 34].

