2.2.2 Correlative Studies Background

An anthropomorphic torso phantom with lung and liver compartments (Data Spectrum Corporation, Durham, North Carolina) was used to assess low-dose imaging capabilities with Y90 (**Figure 1**). Initially, 10.9 mCi of liquid Y90 HCL was injected into the liver compartment with an additional 2.9 mCi in two fillable spheres mounted in the liver to simulate liver tumors. Total liver activity was 13.8 mCi. Lung compartments were filled with a mixture of Styrofoam beads and a Y90 HCL solution with a total activity of 1.12 mCi. **This gave a true LSF of 7.5% and a TNR of 10.** The phantom was imaged using our planar imaging protocol for shunt calculations and with our SPECT/CT protocol for Y90. Energy windows were chosen for quantitative Y90 Bremsstrahlung imaging. Planar imaging (as clinically used for the MAA shunt studies) yielded 6.4% LSF. On the other hand, SPECT calculation of the lung shunt was 6.9%.

SPECT/CT depicted the distribution of activity in the phantom and gave TNR of 6. The PET/CT images on the other hand had very few counts in both the liver and lungs due to the small number of positron emissions by low-dose Y90. Nevertheless, the TNR measured by PET was very accurate at 10 and the LSF was measured at 4.9%. **As depicted by our phantom study results, each imaging modality in the setting of low-dose Y90 have advantages and disadvantages. While PET appears to be accurately measuring TNR, Bremsstrahlung SPECT appears to be more accurate in estimating LSF. Our goal through the proposed study is to ultimately optimize and validate low-dose Y90 PET and/or SPECT as the single study needed to accurately plan Y90 therapy based on institutional availability.**

[figure not shown]

Figure 1 shows images used in the phantom analysis: A) Planar (static image), B) SPECT coronal, C) CT coronal, D) PET coronal.

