7.1.2 Dosing and Administration

Treatment will be administered on an *outpatient* basis. Reported adverse events and potential risks are described in Section 7. Appropriate dose modifications are described in Section 8. No investigational or commercial agents or therapies other than those described below may be administered with the intent to treat the patient's malignancy.

No dose escalation or dose expansion is planned in this procedure.

The treatment Y90 dose will be calculated using the partition model as detailed below:

The required therapeutic Y90 dose will be calculated using MAA SPECT, Y90 SPECT and Y90 PET. **Although all 3 sets of calculations will be made prospectively, the activity calculation based on MAA SPECT (the standard of care) will be used for actual treatment planning.** The activities calculated using Y90 SPECT and PET will be used for post-hoc analysis. Partition model to achieve cytotoxic Target Tumor Dose of >100 Gy will be utilized using the following formulas[7]:

- 1) **Desired Tumor Activity (GBq) = (100 Gy X Tumor Mass (Kg)) / 50**
- 2) **Targeted Normal Liver Activity (GBq) = Desired Tumor Activity (GBq) / TNR**
- 3) **Targeted Liver Lobe Activity (GBq) = (Targeted Normal Liver Activity + Desired Tumor Activity) (GBq)**
- 4) **Targeted Liver Lobe Dose (Gy) = Targeted Liver Dose Activity (GBq) X 50 / Liver mass (Kg)**

The liver and tumor mass will be determined using the volumes calculated by MIM software and assuming density of 1.03 g/cm³ [39]. It will be ensured that targeted liver dose remains below 50 Gy which has been shown to be safe with no sequela of radiation induced liver disease while ensuring the target tumor dose >100 Gy[7, 26].

5) Y90 Activity for administration (GBq) = Targeted Liver Lobe Activity (GBq) X (1+LSF)

Lung dose after therapeutic Y90 RE will be calculated using the following formula:

6) Lung Dose (Gy) = Y90 Activity to be Administered (GBq) X LSF X 50 / Mass of Lungs (Kg)

Lung Dose <30Gy will be ensured by reducing administered activity if needed (lung mass assumed at 1 Kg)[8].

The MAA, low-dose and therapeutic dose Y90 microspheres will be administered intra-arterially using the following technique:

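### TNR has two incompatible meanings: dosing formula 2 needs a ratio of total activities, and the phantom TNR cannot be one

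*Combined protocol and SAP*

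**What the plan says.** Section 7.1.2, repeated in 8.1 G, builds the prescribed activity in steps. Formula 1 gives the tumor activity for 100 Gy. Formula 2 is "Targeted Normal Liver Activity (GBq) = Desired Tumor Activity (GBq) / TNR". Formula 3 adds the two activities, and formula 5 scales the sum for lung shunt. Formulas 4 and 6 give liver and lung doses, which are held below 50 and 30 Gy. All three calculations (MAA SPECT, Y90 SPECT, Y90 PET) use these formulas, and the MAA one sets the treatment.

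The phantom work in 2.2.2 describes the filling: "Initially, 10.9 mCi of liquid Y90 HCL was injected into the liver compartment with an additional 2.9 mCi in two fillable spheres mounted". It continues: "This gave a true LSF of 7.5% and a TNR of 10". Against that true value, "SPECT/CT depicted the distribution of activity in the phantom and gave TNR of 6", and "Nevertheless, the TNR measured by PET was very accurate at 10 and the LSF was measured at 4.9" percent.

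Section 2.1 says the partition model assumes MAA "to distribute uniformly within the liver tumor and NTL, but at different concentrations". The synopsis expands the term only as "tumor to normal liver activity ratio (TNR) will be compared to that of low-dose Y90", and does not say whether activity is total or per unit mass.

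**The concern.** Formula 2 turns a total tumor activity in GBq into a total normal-liver activity in GBq, and formula 3 adds them. With no mass in the formula, TNR there must be a ratio of whole-compartment activities. The phantom TNR in the same protocol is not that ratio. One symbol therefore carries two meanings, and the text does not settle which is entered for a patient.

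Formulas 1 to 5 set the activity each patient receives, and the two meanings give different activities for the same patient. If the concentration ratio is entered, the prescription can fall short of the protocol's own tumor target. The checks in formulas 4 and 6 are upper limits, so they would not flag a shortfall before treatment.

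**Working it through.** **Phantom (2.2.2).** Inputs: spheres 2.9 mCi, liver background 10.9 mCi, lungs 1.12 mCi.

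- LSF = 1.12 / (2.9 + 10.9 + 1.12) = 7.5%. This reproduces the stated value, so the activities are read correctly.
- Total-activity ratio = 2.9 / 10.9 = 0.27. The stated true TNR is 10.
- Formula 2 with TNR 10 gives 2.9 / 10 = 0.29 mCi of background. The phantom held 10.9 mCi.
- A concentration ratio of 10 needs a liver-to-sphere mass ratio of 10 × 10.9 / 2.9 = 37.6. The fill volumes are not given, so this is the natural reading but is unconfirmed.

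**What a concentration TNR would do in formula 2.** Let M_T and M_N be tumor and perfused normal-liver mass.

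- Formula 1: A_T = 100 × M_T / 50.
- As written: A = A_T × (1 + 1/TNR).
- With the mass term: A = A_T × (1 + (M_N/M_T)/TNR).
- Tumor dose from the as-written activity = 100 × (as written / with mass term).

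Inputs from the protocol: largest lesion 7 cm and up to three lesions (5.1), density 1.03 g/cm³ (7.1.2), TNR 5.4 with SD 2.1 (10.2). A 7 cm sphere weighs 0.185 kg and three weigh 0.555 kg. The protocol gives no normal-liver mass. Delivery is to a right or left hepatic artery branch, so I assume 0.4, 0.8 and 1.2 kg. The 5.4 is itself not stated to be a concentration ratio. The last column applies formula 4 to the mass-term activity, taking liver mass as tumor plus normal lobe.

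| Lesions | M_N (kg) | As written (GBq) | With mass term (GBq) | Ratio | Tumor dose, as written (Gy) | Formula 4, mass term (Gy) |
|---|---|---|---|---|---|---|
| One 7 cm | 0.4 | 0.438 | 0.518 | 1.18 | 84.6 | 44.3 |
| One 7 cm | 0.8 | 0.438 | 0.666 | 1.52 | 65.8 | 33.8 |
| One 7 cm | 1.2 | 0.438 | 0.814 | 1.86 | 53.8 | 29.4 |
| Three 7 cm | 0.4 | 1.315 | 1.258 | 0.96 | 104.6 | 65.9 |
| Three 7 cm | 0.8 | 1.315 | 1.406 | 1.07 | 93.5 | 51.9 |
| Three 7 cm | 1.2 | 1.315 | 1.554 | 1.18 | 84.6 | 44.3 |

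These tumor doses are before formula 5, whose factor (1 + LSF)(1 − LSF) = 0.986 at LSF 11.66% is ignored. There is no error when M_N equals M_T, and a slight excess when tumor is heavier. With TNR from 3.3 to 7.5 (5.4 ± 2.1), the ratios run 1.14 to 2.28 (88 to 44 Gy) for one lesion and 0.94 to 1.27 (107 to 79 Gy) for three. For small lesions the ratios are larger but the amounts are small. At 0.8 kg and TNR 5.4, 3 cm needs 8.8 mCi against 0.9 as written, and 5 cm needs 11.7 against 4.3. All are below the 15 mCi planning dose.

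**Planning dose.** 15 mCi is 0.555 GBq. At LSF 11.66% and TNR 5.4 it gives the tumor 0.555 × 0.8834 × 50 × TNR / (TNR × M_T + M_N): 95, 74 and 60 Gy for one lesion, and 39, 35 and 32 Gy for three. Added to the as-written therapy, the totals are 179, 139 and 114 Gy, and 144, 128 and 116 Gy.

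**Liver limit.** The planning dose adds 0.555 × 0.8834 × 50 = 24.5 Gy·kg, divided by lobe mass. Mass-term totals become 86, 59 and 47 Gy for one lesion and 92, 70 and 58 Gy for three, so five of the six pass 50 Gy if the planning dose counts.

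**The case against.** The patient-facing wording has a consistent literal reading. TNR is called an activity ratio, formulas 1 to 3 use activity for totals in GBq, and 8.1 E says only each compartment's share of activity is needed. On that reading formula 2 is correct. The phantom is background work with Y90 only, while treatment is set from MAA SPECT. The text between 2.1 and 2.2.2 and reference 7, cited for the formulas, were not available to me, and either may define TNR. Section 8.1 K measures tumor dose by PET/CT the same week, and 13.2 has data reviewed monthly or every four patients, so a systematic shortfall could be noticed early.

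Most of this stands as a limit on the claim. It does not remove the conflict. No single definition of TNR fits both formula 2 and the phantom: if TNR is a total ratio, the phantom tested a different quantity under the same name; if it is a concentration ratio, formula 2 lacks its mass term. The phantom also bears on the modalities behind two of the three patient calculations. Measurement after treatment protects later patients more than the one treated, since 2.1 notes that retreatment for inadequate dose is rare.

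A reader might infer that patients will be underdosed, or that formula 2 is a plain arithmetic error. The documents support neither, because they do not show that a concentration ratio is entered. Nor do they support a cumulative shortfall: at TNR 5.4 the planning dose brings every example above 100 Gy. The 105 Gy example (three lesions, 0.4 kg) is also not a plan that could be given unmodified, since as written formula 4 gives 1.315 × 50 / 0.955 = 69 Gy.

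**Conclusion.** The point holds as an internal conflict in a stated dosing rule. Formula 2 needs a total-activity ratio, and the protocol's own phantom TNR of 10 cannot be one, because the activities give 0.27.

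The dosing consequence is conditional on a concentration TNR being entered, on TNR 5.4 being such a ratio, and on assumed normal-liver masses. On those terms the therapeutic administration alone delivers about 85, 66 or 54 Gy to one 7 cm lesion, against a target above 100 Gy. For three such lesions the activity needed is only 0.96 to 1.18 times the as-written value.

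The primary paired t-tests on LSF and TNR do not use formula 2 and are unaffected. Delivered dose and the dose-response threshold are affected only if 8.1 K reuses formula 2, and that step starts from measured PET/CT. This should be fixed before dosing; it is not a proven error in the prescription.

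**What to change.** Define TNR once, as the tumor-to-normal-liver activity concentration ratio per unit mass. In 7.1.2 and 8.1 G write formula 2 as A_N = A_T × (M_N / M_T) / TNR. If the sponsor confirms that a total-activity ratio is intended, keep formula 2, say so, and give the phantom quantity another name.

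Confirm, rather than assume, which definition lies behind the 5.4 (2.1) planning value and the calculation in 8.1 K. Check the recorded phantom fill volumes: a concentration TNR of 10 requires the mass ratio of 37.6, and only the volumes can test it.

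Recheck mass-term activities against the 50 Gy liver and 30 Gy lung limits. State whether formula 4's liver mass includes tumor and whether the 15 mCi planning dose counts. On the tumor-plus-normal-lobe reading the liver limit would bind in some cases, for example 51.9 Gy for three 7 cm lesions at 0.8 kg before the planning dose.

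The cost is a wording change in two places and a physics check on existing data, with no extra patients or procedures. Supply is adequate in these examples at TNR 5.4 and LSF 11.66%. The largest mass-term activity is 1.554 × 1.1166 = 1.735 GBq, or 46.9 mCi, against 83 mCi left on Thursday (7.2.4). Its lung dose is 1.735 × 0.1166 × 50 = 10.1 Gy, plus 0.555 × 0.1166 × 50 = 3.2 Gy from the planning dose. The real cost may be that the liver limit, not the tumor target, sets the activity in some patients, and the protocol should say what happens then.

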These problems can be overcome by using a radioactive tracer in pre-treatment planning that is bioidentical to Y90 microspheres, which is the principle behind shunt study and treatment with Holmium-166 microspheres (¹⁶⁶Ho)[38]. Currently, ¹⁶⁶Ho is not available in the United States, and low-dose Y90 microspheres are the most readily available direct surrogate to predict LSF and tumor dose. Similar to the use of low-dose ¹⁶⁶Ho for treatment planning, a prospective personalized dosimetry method using direct yet non-toxic surrogate for therapeutic Y90 microspheres is necessary to further optimize Y90 dosimetry in a clinically pertinent manner. We believe that such efforts will not only standardize Y90 RE methodology and improve post Y90 RE outcomes under currently recommended indications but will also better allow accurate study of further indications. Additionally, LSF is a major determinant in the calculation of a safe Y90 dose as LSF > 20% is a relative contraindication to Y90 RE. Hence, it is possible that patients with inaccurately high LSF's estimated by MAA may receive lower suboptimal Y90 therapeutic doses or are entirely excluded from treatment, thus adversely impacting post-Y90 outcomes.

In summary, there is growing evidence that factoring individual patient characteristics into Y90 treatment planning are likely to significantly impact both TR and treatment tolerability. To this end, the partition model, while more resource intensive, has made great strides towards treatment individualization. However, the use of MAA in predicting post Y90 RE absorbed dose and

biodistribution is flawed and inaccurate, leading to suboptimal dose delivery, unnecessary hepatotoxicity and poor outcomes. **Therefore, we propose low-dose Y90 microspheres for therapy planning, as an alternative to MAA, to be a bioidentical therapeutic Y90 surrogate marker to better predict and thus achieve optimal therapeutic dosing.** Our long-term goal is to improve TR, PFS, and OS while reducing potential associated toxicities in patients treated with Y90 RE.

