4.3 Justification for Dose

Based on our phantom study to minimize scatter on SPECT/CT and to ensure adequate activity to be imaged using PET, 15 mCi of low-dose Y90 is found to be adequate. Additionally, in a hypothetical patient with a LSF of 100% (usually ~10% in HCC patients), 15 mCi of Y90 activity will result in 27.8 Gy of radiation to the lungs which is within the accepted limits of 30 Gy per treatment session. Such patient will not be a candidate a for therapeutic Y90 dose so cumulative dose to the lungs will remain below 30 Gy.

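### The 50 Gy liver and 30 Gy lung checks before therapy leave out the 15 mCi planning Y90 already given through the same branches

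*Combined protocol and SAP*

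**What the plan says.** Section 7.1.1 fixes the planning activity at 15 mCi for every patient. Section 8.1 D gives it on Monday through the branches used for MAA. Section 8.1 H gives the therapy on Wednesday or Thursday of the same week with the same catheter technique, taken here to mean the same branches.

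The therapeutic activity is built in 7.1.2 (repeated in 8.1 G) from a 100 Gy tumor target. Formula 2 is "Targeted Normal Liver Activity (GBq) = Desired Tumor Activity (GBq) / TNR", and formula 3 adds tumor and normal-liver activity. Formula 4 converts the sum to a dose: "Targeted Liver Lobe Dose (Gy) = Targeted Liver Dose Activity (GBq) X 50 / Liver mass (Kg". The limit follows: "It will be ensured that targeted liver dose remains below 50 Gy which has been shown to be safe". Formula 6 is introduced with "Lung dose after therapeutic Y90 RE will be calculated using the following formula". It uses only the activity still to be administered and is checked against 30 Gy with a 1 kg lung mass.

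Section 7.1.3 adjusts the therapeutic dose when LSF is 20% or more and does not mention the planning activity. Activities calculated from the planning Y90 images are kept for post-hoc analysis.

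Other sections bear on the total:

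- Section 4.3 considers a hypothetical patient with LSF 100% and concludes: "Such patient will not be a candidate a for therapeutic Y90 dose so cumulative dose to the lungs will remain below 30 Gy". It calls 30 Gy a limit per treatment session.
- Section 11.1 states the 30 Gy lung limit without that qualifier.
- Section 8.1 K calculates the dose delivered to tumor, normal liver and lung on Friday, after therapy.
- No cumulative liver limit appears in the text available for review.

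**The concern.** The planning injection is the trial's one added intervention, and safety is part of the primary objective. Both checks are there to hold dose under a stated limit before therapy is given, yet neither contains activity that is already in the patient and whose amount is known. The one cumulative statement, in 4.3, is about a patient who is never treated, so it gives no assurance for those who are. At stake is whether a lobe can pass the written check while the same quantity, summed over about three days, is above its limit, without that total being seen before therapy or reported in the safety analysis.

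**Working it through.** **Inputs.** Planning activity P = 15 mCi (7.1.1). Conversion factor 50, tissue density 1.03 g/cm³ and lung mass 1 kg (7.1.2). TNR 5.4 (10.2). LSF 10% (4.3, typical value). Largest eligible lesion 7 cm, at most three (5.1). Y90 half-life 64.1 h (7.2.4). Lobe mass is not given; 0.75, 1.0 and 1.5 kg are assumptions.

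**1. The plan's own figure.** P = 15 × 0.037 = 0.555 GBq. At LSF 100%, formula 6 gives 0.555 × 1 × 50 / 1 = 27.75 Gy, which matches the 27.8 Gy in 4.3.

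**2. What planning adds to the lobe.** P × (1 − LSF) = 0.555 × 0.9 = 0.4995 GBq. Times 50 and divided by lobe mass, this is 33.3, 25.0 and 16.7 Gy at 0.75, 1.0 and 1.5 kg.

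**3. The written check, one 7 cm lesion.** Tumor mass: (4/3)π × 3.5³ × 1.03 / 1000 = 0.185 kg. Formula 1: 100 × 0.185 / 50 = 0.370 GBq. Formula 2: 0.370 / 5.4 = 0.0685 GBq. Formula 3: 0.438 GBq.

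**4. TNR as a concentration ratio.** Formula 2 treats TNR as a ratio of activities. The phantom in 2.2.2 does not: "10.9 mCi of liquid Y90 HCL was injected into the liver compartment with an additional 2.9 mCi in two fillable spheres", and "This gave a true LSF of 7.5% and a TNR of 10", although 2.9 / 10.9 is 0.27. Both readings are therefore shown. By concentration, normal-liver activity = (0.370 / 0.185) / 5.4 × (lobe mass − 0.185), and lobe activity is 0.579, 0.672 and 0.857 GBq at the three masses.

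| Lobe mass (assumed) | Formula 2: check → total | Concentration: check → total |
|---|---|---|
| 0.75 kg | 29.2 → 62.5 Gy | 38.6 → 71.9 Gy |
| 1.0 kg | 21.9 → 46.9 Gy | 33.6 → 58.6 Gy |
| 1.5 kg | 14.6 → 31.3 Gy | 28.6 → 45.2 Gy |

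By formula 2, the written check is met above 0.44 kg and the total only above 0.94 kg (0.438 + 0.4995). By concentration the two masses are 0.48 and 1.27 kg.

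**5. Normal liver alone, 0.75 kg lobe (planning + therapy).** Formula 2: 6.9 + 6.1 = 13.0 Gy. Concentration: 16.0 + 18.5 = 34.5 Gy.

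**6. If liver mass means the whole liver** (1.5 kg assumed, 0.75 kg lobe treated): (0.438 + 0.4995) × 50 / 1.5 = 31.3 Gy, or (0.579 + 0.4995) × 50 / 1.5 = 36.0 Gy.

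**7. Lung.** Planning adds 27.75 × LSF: 2.8 Gy at 10% and 5.6 Gy at 20%.

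- One 7 cm lesion, LSF 10%: formula 5 gives 0.438 × 1.1 = 0.482 GBq. Formula 6 gives 2.4 Gy, and the total is 5.2 Gy.
- Three 7 cm lesions, LSF 20%, formula 2: lobe activity 1.315 GBq, lung dose 15.8 + 5.55 = 21.3 Gy.
- For those three lesions the total reaches 30 Gy at LSF 27.0%, and formula 6 alone reaches it at 34.0%. Only between these values does the omission change the answer (25.2% to 31.3% by concentration at 1.5 kg).

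**The case against.** The strongest reply is that the liver figures above 50 Gy are not normal-tissue doses. They are lobe averages that include a tumor meant to receive more than 100 Gy. Section 7.1.2 ties 50 Gy to radiation-induced liver disease, and 11.1 attributes that disease to excess dose in normal parenchyma. In the worst example normal liver totals 13.0 or 34.5 Gy. This stands. A reader might infer that the plan lets normal liver exceed 50 Gy or exposes patients to shown harm, and the documents support neither. The point is narrower: formula 4, the quantity the plan chose to limit, is checked on part of the activity.

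Second, the excess depends on assumptions: the largest lesion and a small lobe. By formula 2 only the 0.75 kg lobe exceeds 50 Gy, and on the whole-liver reading neither total does. This also stands, and it limits the point to a few patients.

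Third, 4.3 calls 30 Gy a per-session limit, so formula 6 could be a deliberate per-session check. That is fair for the lung, but 11.1 has no such qualifier and no per-session statement exists for the liver. It would also be wrong to say that 4.3 contradicts the checks: its cumulative claim is correct for the untreated patient it describes.

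Fourth, a serious lung problem might be inferred, and the numbers do not show one. Section 2.1 already says "LSF > 20% is a relative contraindication to Y90 RE", and 7.1.3 modifies the dose at high shunt.

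Finally, 8.1 K calculates delivered dose and the planning scans exist, so the data for a cumulative figure are collected. But step K comes after therapy and does not call for adding the planning dose.

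**Conclusion.** The omission holds on the text: the checks in 7.1.2 and 8.1 G have no term for the 0.555 GBq already given, and 7.1.3 adjusts only the therapeutic dose. By the protocol's own conversion, at LSF 10%, it is worth about 33, 25 or 17 Gy of lobe-average dose for a 0.75, 1.0 or 1.5 kg lobe, against a limit of 50 Gy. With one 7 cm lesion in a 0.75 kg lobe, a plan reading 29.2 Gy (38.6 by concentration) totals 62.5 Gy (71.9). The lung effect matters only where the 30 Gy check is close to binding, that is, with high shunt and a large therapeutic activity.

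This rests on the assumed lobe masses, on all planning activity staying in the treated lobe and lungs, and on therapy using the same branches. It is an omission rather than a contradiction, and no toxicity follows from it. It is a cheap improvement. How TNR and liver mass are defined is a separate matter; the two readings only set the range here.

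**What to change.** Let P be the planning activity actually given (0.555 GBq as planned), and use the MAA LSF so that prescribing stays on MAA. In 7.1.2 and 8.1 G, before therapy:

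- Liver: (Targeted Liver Lobe Activity + P × (1 − LSF)) × 50 / Liver mass, against 50 Gy.
- Lung: (Y90 Activity to be Administered + P) × LSF × 50 / Mass of Lungs, against 30 Gy.
- Apply the same lung total in 7.1.3.
- Report cumulative lobe, non-tumoral liver and lung dose per patient in the 10.5 safety tables.

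The reporting must avoid double counting, because part of the planning activity is still present on the post-therapy PET. If therapy dose is the measured proportion times the therapeutic activity, add the whole planning dose. If the PET is read as absolute activity, add only the part delivered before therapy: 1 − 2^(−48/64.1) = 40% on Wednesday, 1 − 2^(−72/64.1) = 54% on Thursday.

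The cost is one term in each of two formulas, wording in 7.1.3 and one dose table, with no new imaging or visits. The real downside is lower therapeutic activity in a few patients with a large lesion in a small lobe, or with high shunt. In the 0.75 kg example the lobe could take 0.75 − 0.4995 = 0.2505 GBq of therapy instead of 0.438 (43% less), or instead of 0.579 by concentration (57% less). In a 0.50 kg lobe at LSF 10% planning alone gives 49.95 Gy, which is better known before the low-dose injection. If the sponsor intends per-session limits, the protocol should say so and still report the totals.

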The patient will then be discharged from IR after removal of the radial sheath according to our standard protocol.

F. Low-dose Y90 PET/CT of chest and abdomen (Monday)

The patient will then undergo time of flight Y90 PET/CT with one or two bed positions depending on the patient's size. This will also occur on the same day and at the same location as the remainder of mapping day either at EUH or EUHM.

Schedule of Mapping Days:

7:30 AM-9:30 AM: 1st Angiographic study for mapping and MAA delivery

10:00 AM-11:00 AM: MAA SPECT/CT (Patient will go to nuclear medicine with radial/femoral arterial access sheath in place)

11:30 AM-1:00 PM: 2nd Angiographic study for low-dose Y90 delivery (After the procedure, patient's femoral sheath will be removed and hemostasis will be achieved with manual compression or closure device. If procedure performed via radial access, which is more commonly performed currently at Emory, the radial sheath will stay in and removed according to IR protocol after Y90 SPECT/CT.)

2:00 PM-3:00 PM: Y90 Bremsstrahlung SPECT/CT

3:00 PM-3:30 PM: Removal of the radial sheath at IR post procedural area and discharge.

4:30-5:30 PM: Y90 PET/CT.

Patient is free to go home after this.

G. Prospective Personalized Targeted Therapeutic Y90 Tumor(s) Dosimetry (Tuesday/Wednesday)

The required therapeutic Y90 dose will be calculated using MAA SPECT, Y90 SPECT and Y90 PET. **Although all 3 sets of calculations will be made prospectively, the activity calculation based on MAA SPECT (the standard of care) will be used for actual treatment planning.** The activities calculated using Y90 SPECT and PET will be used for post-hoc analysis. Partition model to achieve cytotoxic Target Tumor Dose of >100 Gy will be utilized using the following formulas[7]:

- i. **Desired Tumor Activity (GBq) = (100 Gy X Tumor Mass (Kg)) / 50**
- ii. **Targeted Normal Liver Activity (GBq) = Desired Tumor Activity (GBq) / TNR**
- iii. **Targeted Liver Lobe Activity (GBq) = (Targeted Normal Liver Activity + Desired Tumor Activity) (GBq)**
- iv. **Targeted Liver Lobe Dose (Gy) = Targeted Liver Dose Activity (GBq) X 50 / Liver mass (Kg)**

The liver and tumor mass will be determined using the volumes calculated by MIM software and assuming density of 1.03 g/cm³^[39]. It will be ensured that targeted liver dose remains below 50 Gy which has been shown to be safe with no sequela of radiation induced liver disease while ensuring the target tumor dose >100 Gy[7, 26].

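### Formulas 5 and 6 do not conserve activity: with LSF as a fraction of total activity, the (1+LSF) step leaves the liver slightly short of its target, by LSF squared

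*Combined protocol and SAP*

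**What the plan says.** Section 7.1.2 of the combined protocol and SAP gives six formulas, and 8.1 G repeats them as i to vi. Their stated purpose is: "Partition model to achieve cytotoxic Target Tumor Dose of >100 Gy will be utilized". The steps that matter here are:

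- Formula 1: "Desired Tumor Activity (GBq) = (100 Gy X Tumor Mass (Kg)) / 50"
- Formula 2: "Targeted Normal Liver Activity (GBq) = Desired Tumor Activity (GBq) / TNR"
- Formula 3: "Targeted Liver Lobe Activity (GBq) = (Targeted Normal Liver Activity + Desired Tumor Activity) (GBq"
- Formula 5: "Y90 Activity for administration (GBq) = Targeted Liver Lobe Activity (GBq) X (1+LSF"
- Formula 6: "Lung Dose (Gy) = Y90 Activity to be Administered (GBq) X LSF X 50 / Mass of Lungs (Kg"

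(The final bracket of formulas 3, 5 and 6 falls outside the quotes.) Lung mass is taken as 1 kg.

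The same text says that the plan keeps the tumor above 100 Gy. Section 7.1.3 softens this to an aim, where possible, once LSF is 20% or more. The calculation is made three times: from MAA SPECT, Y90 SPECT and Y90 PET. The MAA result sets the treatment; the two Y90 results are kept for post-hoc analysis.

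**The concern.** Formula 5 adds an allowance of L x LSF to cover what is lost to the lungs. Formula 6 then takes LSF of the larger, administered activity, which is L x (1+LSF) x LSF. The allowance is smaller than the loss, so lobe target plus lung activity comes to more than was administered. Formulas 1 to 3, 5 and 6 cannot all hold for any LSF above zero.

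At stake is whether the activity that the plan prescribes matches the tumor dose that the plan says it achieves. The mismatch sits in the formula that sets the treatment activity for every patient, and it carries into the two sets of Y90-based activities reserved for post-hoc work.

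**Working it through.** **1. What LSF means in this plan.** Formula 5 would balance exactly if LSF meant lung activity divided by liver activity. Three places show that it does not.

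- Section 4.3: 15 mCi x 0.037 GBq/mCi = 0.555 GBq. Formula 6 at LSF 100% gives 0.555 x 1.00 x 50 / 1 = 27.75 Gy, which reproduces the stated 27.8 Gy. All the activity is in the lungs. As a lung-to-liver ratio, 100% would put half of it there, 27.75 / 2 = 13.9 Gy.
- Section 2.2.2, phantom: lung 1.12 mCi, liver 13.8 mCi. As a fraction of the total, 1.12 / (1.12 + 13.8) = 1.12 / 14.92 = 7.51%, matching the stated 7.5%. As a ratio, 1.12 / 13.8 = 8.12%, which does not match.
- Formula 6 itself multiplies the whole administered activity by LSF.

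**2. Activity balance.** With L from formula 3:

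- administered = L x (1+LSF)
- lungs = L x (1+LSF) x LSF
- left in the liver = L x (1+LSF) x (1-LSF) = L x (1-LSF²)
- lobe target plus lungs, minus administered = L x LSF²

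Formulas 1 and 2 fix the tumor's share of the liver activity at TNR / (TNR + 1). The tumor dose therefore scales with what the liver keeps, and the implied planned dose is 100 x (1-LSF²) Gy.

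**3. Results, with L = 1.**

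| LSF | Administered | Lungs | Left in liver | Excess over administered | Implied tumor dose (Gy) |
|---|---|---|---|---|---|
| 0% | 1.0000 | 0 | 1.0000 | 0 | 100.00 |
| 10% | 1.1000 | 0.1100 | 0.9900 | 0.0100 | 99.00 |
| 11.66% (MAA mean assumed in 10.2) | 1.1166 | 0.1302 | 0.9864 | 0.0136 | 98.64 |
| 15% | 1.1500 | 0.1725 | 0.9775 | 0.0225 | 97.75 |
| 20% | 1.2000 | 0.2400 | 0.9600 | 0.0400 | 96.00 |

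**4. One case followed through.** Assume a tumor of 0.1 kg, TNR 5.4 (the MAA mean in 10.2) and LSF 11.66%.

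- Tumor activity: 100 x 0.1 / 50 = 0.2 GBq
- Normal liver activity: 0.2 / 5.4 = 0.0370 GBq
- Lobe: 0.2370 GBq
- Administered: 0.2370 x 1.1166 = 0.2647 GBq
- Lungs: 0.2647 x 0.1166 = 0.0309 GBq, leaving 0.2338 GBq in the liver
- Tumor dose: 0.2338 x (5.4 / 6.4) x 50 / 0.1 = 98.6 Gy, in agreement with the table

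**The case against.** The strongest reply is that this is a rounding-sized residual with little consequence. Most of that stands.

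- **Size.** The shortfall is 1.0 Gy at LSF 10%, about 1.4 Gy at the assumed mean and under 4 Gy below 20%. The phantom in 2.2.2 shows much larger measurement error: SPECT TNR 6 against a true 10, and PET LSF 4.9% against 7.5%.
- **Cause.** A reader might infer that the (1+LSF) step alone defeats the >100 Gy target. It does not: formula 1 is set for exactly 100 Gy, so the strict inequality already fails at LSF 0. From LSF 20% upward, 7.1.3 has qualified the target.
- **Planned is not delivered.** A reader might infer that patients will in fact receive less than 100 Gy. If true Y90 LSF is half the MAA value, as 10.2 assumes, and the tumor-to-liver split is unchanged, the liver keeps 1.1166 x (1 - 0.0583) = 1.05 of its target, or about 105 Gy to the tumor. The formulas also leave out tumor dose from the 15 mCi mapping administration into the same branches.
- **Tracer comparison.** A reader might infer a bias against MAA, since the residual is 4% at LSF 20% and 1% at 10%. The documents do not support this. The primary tests in 10.3 compare LSF and TNR directly and never pass through formula 5. Formulas 1 to 5 run from a fixed dose to a required activity. To get dose from a known administered activity, 8.1 E says the compartment proportions suffice. Section 10 contains no analysis of the formula 5 activities.
- **Lung limit.** Formula 6 starts from the activity to be administered, so the 30 Gy check is not distorted.
- **Formula 2.** The phantom has TNR 10 with 2.9 mCi in the spheres and 10.9 mCi in the liver, an activity ratio of 0.27. TNR is therefore a concentration ratio there, yet formula 2 has no mass term. On that reading the case in step 4, with an assumed normal lobe mass of 0.3 to 0.8 kg, gives a tumor share of 0.54 / (0.54 + mass) and about 75 to 47 Gy. That separate mismatch could far outweigh this one.

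What the reply does not remove is the contradiction itself. A formula that sets the administered activity disagrees with the next formula and with the stated target.

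**Conclusion.** The inconsistency is real and follows from the plan's own figures. Under formulas 1 to 3, 5 and 6, the liver keeps 1-LSF² of its target. The implied planned tumor dose falls short of 100 Gy by 100 x LSF² Gy, small at typical LSF and 4.0 Gy at 20%.

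The Gy figures rest on three conditions: LSF is a fraction of total activity, formula 2 is taken as written, and only the therapeutic administration is counted, before any reduction for the lung limit. What is affected is the activity from formula 5, used for treatment planning (MAA) and held for post-hoc analysis (Y90 SPECT and PET). The point does not extend to the primary endpoints or to the dose that patients receive.

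**What to change.** The sponsor should reconcile formulas 5 and 6 in 7.1.2, and v and vi in 8.1, with each other, with the definition of LSF implied by 2.2.2 and 4.3, and with the >100 Gy statements in 7.1.2, 7.1.3 and 8.1 G. The test is that liver plus lung activity equals administered activity at any LSF. LSF should be defined once in words. The one reconciled set should then serve all three activity calculations (MAA SPECT, Y90 SPECT, Y90 PET). Which dose, target or formula to adopt is for the sponsor; none is proposed here.

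The cost is a text correction in those sections and a check of the spreadsheet or software that carries out the calculation. Sample size, visits and the primary analysis do not change.
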